## Rationale

Over the past 45 years, more than 70,000 patients with breast cancer (BC) have been included in GBG studies. These prospective clinical trials consistently evaluate long-term outcomes such as recurrences, deaths, and late-onset toxicities as primary or secondary objectives. However, for administrative and financial reasons, follow-up is typically limited to 1–5 years. Moreover, clinical trials increasingly demand significant effort from trial sites yet are challenged by limited resources. Recent publications have revealed that, in early BC setting, regular follow-up duration in clinical trials is not sufficient to capture late events, especially in Estrogen Receptor (ER)-positive disease. This is caused by the intrinsic characteristics of the disease and the increasing complexity of adjuvant endocrine therapies, as well as enhanced treatment options in the metastatic setting.

Unlike many other diseases, breast cancer recurs at a significant rate (approximately 2-4% per year) even 20 years after initial treatment. The effects of therapy are often only evident after a long period of observation, particularly in patients with ER-positive tumors. For example, the improvement in survival rates achieved through breast radiation therapy only becomes apparent after 15 years. This underlines the importance of long-term follow-up to fully capture treatment efficacy and late side effects. The relevance of long-term observation has been repeatedly emphasized by international research groups, such as the Early Breast Cancer Trialists' Collaborative Group. Although the long-term course with the collection of data on recurrences, deaths, and late toxicities is the primary or at least secondary endpoint in all prospective treatment studies conducted by the GBG, follow-up observation is usually limited to 1-5 years for administrative reasons.

National and international experience shows that contact with study participants is often lost during the follow-up phase of a clinical trial without them expressly withdrawing their consent. Due to the decentralized healthcare structure and increasing staff and financial constraints, primary care clinics are no longer able to fulfill the task of long-term follow-up care. This is also not considered to be the responsibility of the cost bearers.

In this respect, other options must be sought to enable long-term observation. Breast cancer patients show above-average compliance with medical and therapeutic measures. In addition, they have a very high level of knowledge about the course of this disease and their individual medical history. A large proportion of patients keep their own patient files, in which they collect all findings relating to their disease, because the highly interdisciplinary nature

of breast cancer means that patients are repeatedly required to report their medical history to new doctors themselves. In this respect, it seems possible to obtain the information necessary for long-term observation through self-reporting by patients.

Evidence also supports the integration of register data with clinical trial results. For example, Shi et al. demonstrated a high level of concordance between cancer register data and randomized trial data, including a 99.0% agreement in disease-free status, thereby indicating the potential of register-based long-term follow-up as a complementary tool to collect data after regular follow up in randomized trials. There have been several initiatives calling for pragmatic clinical trials that put patient engagement in the center, address clinically relevant questions in broad, representative populations and are embedded in clinical practice. Such trials may offer a valuable framework for addressing the limitations of traditional explanatory trials, particularly in oncology where long-term, patient-centric outcomes are essential. These trials are designed to reflect routine clinical practice, using broad eligibility criteria, decentralized settings, and streamlined data collection methods, making them well-suited for long-term follow-up and real-world evidence generation.

To address these gaps, the GBG established a multicenter, non-interventional, long-term cancer register study to follow-up former clinical trial participants collecting patient-reported outcomes and other relevant data beyond the end of the original study protocol. By leveraging patient engagement and longitudinal data collection, this initiative aims to generate real-world evidence for improved clinical decision-making.

## Objectives and endpoints of the survey

The primary objective of the register study is to collect long-term follow up data from clinical cancer trial participants beyond the end of study to evaluate long-term survival outcomes. These outcomes will be evaluated with the following endpoints:

- Disease-free survival (DFS) which is defined as the time from randomization to the first occurrence of local (invasive or DCIS) or regional recurrence of the original cancer, contralateral breast cancer (invasive or DCIS) distant recurrence, diagnosis of a second primary invasive cancer (other than the index cancer type), or death from any cause, whichever occurs first.
- Invasive disease-free survival (iDFS) which is defined as the time from randomization to the first occurrence of any invasive local or regional recurrence, invasive contralateral breast cancer, distant recurrence, diagnosis of an invasive second

primary cancer (other than the index cancer type), or death from any cause, whichever occurs first.

- Distant disease-free survival (DDFS) is defined as the time from randomization to the first occurrence of distant recurrence, diagnosis of a second primary invasive cancer (other than the index cancer type), or death from any cause, whichever occurs first.
- Locoregional invasive recurrences-free interval (LRRFI) is defined as the time from randomization to the first occurrence of any invasive loco-regional recurrence (including recurrence in the primary tumor site or associated regional lymph nodes), or any invasive contralateral breast cancer, whichever occurs first; distant recurrence, invasive second primary cancer (other than the index cancer type), or death from any cause are considered competing events.
- Overall survival (OS) is defined as the time from randomization to death of any cause.
- Other study-specific or adapted long-term survival endpoints may be defined in the respective study protocol or statistical analysis plan (SAP), tailored to the study population and tumor type.

Secondary Endpoints may include:

- Long-term side-effects associated with study therapy.
- Subsequent anti-cancer therapies administered after study completion.
- Pregnancies occurring after study participation and evaluate their outcomes.
- Quality of life (QoL) post-study.
- Additional study-specific long-term outcomes as defined in the respective study protocol or statistical analysis plan (SAP), tailored to the study population and tumor type.

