### ***Data collected***

The names and contact details of the participants in the long-term observation study will be recorded by the data trustee. At the participant's request, the name and contact details of a contact person of her/his choice can also be recorded, who will be contacted instead and provided with information about the participant's state of health (see "Change of address"

form). Only the data trustee has access to this data. Data will be stored until withdrawal of consent.

The participants are asked to provide information about their health status with regard to their long-term outcomes of their cancer disease and associated medical data. Among other questions they are asked about relevant medical follow up information related to the cancer diagnosis or cancer treatment received e.g. any recurrences or distant metastases, any new cancers or pregnancies (see the "Medical data" form).

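### DFS, iDFS and DDFS count any second primary invasive cancer outside the index type, so an invasive basal- or squamous-cell skin carcinoma is an event, and it competes with LRRFI

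*Protocol*

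**What the plan says.** The Protocol's primary objective is long-term survival outcome, and it introduces the endpoint list with "These outcomes will be evaluated with the following endpoints". Four of the five listed endpoints refer to second primaries:

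- **DFS and DDFS** both end in "diagnosis of a second primary invasive cancer (other than the index cancer type), or death from any cause". For DDFS the full event list is "first occurrence of distant recurrence, diagnosis of a second primary invasive cancer (other than the index cancer type), or death from any cause".
- **iDFS** has the same component in a different word order, "invasive contralateral breast cancer, distant recurrence, diagnosis of an invasive second", and continues to the same bracketed carve-out.
- **LRRFI** does not count second primaries as events but treats them as competing: "distant recurrence, invasive second primary cancer (other than the index cancer type), or death from any cause are considered competing events".

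The list closes by allowing additions elsewhere: "Other study-specific or adapted long-term survival endpoints may be defined in the respective study protocol or statistical analysis plan (SAP".

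The section Data collected says that participants are asked, among other things, about "any recurrences or distant metastases, any new cancers or pregnancies". The Study Overview plans no definite end to the register. The Risk Benefit Assessment keeps participants in it until withdrawal, death or loss to follow-up. The Rationale looks to 15 and 20 years.

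**The concern.** The definitions work at component level: they separate DCIS from invasive disease and name one type of second primary that does not count. Nothing in them, or elsewhere in the Protocol, takes out skin carcinoma. The word invasive removes in-situ skin lesions but not invasive basal- or squamous-cell carcinoma.

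A participant with such a tumour and no sign of the original cancer would thus lose disease-free status on three endpoints of the primary objective. The oddest case is DDFS, where a local skin tumour counts alongside distant recurrence. For LRRFI the tumour is a competing first event, so a locoregional recurrence that follows it is not counted.

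What is at stake is how the reported event rates are read. The register is meant to describe the late course of the index disease and to inform counselling. Over open-ended follow-up, with a question that invites reports of any new cancer, these events add up and push the curves away from that purpose.

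**Working it through.** The Protocol states no event count, event rate by endpoint or sample size calculation, so there is no figure of its own to reproduce. The check has a textual part and an illustration of size.

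**Text.** The four definitions were compared. Each has exactly two qualifiers on the second-primary component: invasive, and not of the index type. A search of all sections for an exclusion of skin, basal-cell, squamous-cell or non-melanoma cancer finds none.

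**Inputs for the size.**
- Base hazard r = 2% or 4% per year: the recurrence range in the Rationale.
- Skin-carcinoma hazard s = 0.2% or 0.5% per year: an assumption, not in the documents.
- Horizon T = 15 years: a time point named in the Rationale.
- Constant hazards and independent competing first events: an assumption.

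**Formulas.**
- Risk without skin carcinoma: F0 = 1 − exp(−rT)
- Risk with skin carcinoma: F1 = 1 − exp(−(r+s)T)
- Proportion whose first event is skin carcinoma: [s/(r+s)] × F1

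**Results at 15 years.**

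| r | s | F0 | F1 | Rise (points) | Relative rise | Skin carcinoma first |
|---|---|---|---|---|---|---|
| 2% | 0.2% | 25.9% | 28.1% | 2.2 | 8.4% | 2.6% |
| 2% | 0.5% | 25.9% | 31.3% | 5.4 | 20.7% | 6.3% |
| 4% | 0.2% | 45.1% | 46.7% | 1.6 | 3.6% | 2.2% |
| 4% | 0.5% | 45.1% | 49.1% | 4.0 | 8.8% | 5.5% |

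For example, with r = 2% and s = 0.5%: F0 = 1 − exp(−0.30) = 25.9%; F1 = 1 − exp(−0.375) = 31.3%; skin carcinoma first = 0.005/0.025 × 31.3% = 6.3%.

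The rise in risk is smaller than the proportion with skin carcinoma first, because some of those participants would have had another event by 15 years anyway.

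**Direction of the remaining error.** The base r covers recurrence only. DFS also counts deaths and other second primaries, so its true base is higher and the added risk smaller. For DFS the table is therefore at the upper end for a given s. The documents give no separate rate for DDFS, so it is not sized here.

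**LRRFI.** Assume 0.5% per year locoregional events and 3% per year other competing events (neither is in the documents). The 15-year cumulative incidence is 0.005/0.035 × (1 − exp(−0.525)) = 5.84%. Adding s gives:
- s = 0.2%: 0.005/0.037 × (1 − exp(−0.555)) = 5.76%, a relative fall of 1.4%.
- s = 0.5%: 0.005/0.040 × (1 − exp(−0.600)) = 5.64%, a relative fall of 3.3%.

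**The case against.** **The adaptation clause.** This is an umbrella register over many parent trials, and the closing bullet lets a study protocol or SAP tailor survival endpoints. Which second primaries count could be settled there. That is a fair point about where detail may go. But the bullet concerns other or adapted endpoints and does not make the five listed definitions provisional. An SAP that excluded skin carcinoma from DFS would depart from DFS as the Protocol writes it.

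**A deliberate choice.** A sponsor may wish to count every second cancer, and nothing in the Protocol contradicts that. It would then need to be stated, since the present text does not address these tumours at all.

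**Stronger readings that a reader might infer, and why they are not supported:**
- *Treatment effects will be diluted.* Population and Statistical Methods describe the analyses as descriptive. The Protocol specifies no hazard ratio, hypothesis or power, so there is no planned contrast to attenuate. The supportable harm is to event rates.
- *Events rise by 5-25%, or 3-7% of participants gain a spurious event.* The first is a ratio of hazards (0.002/0.04 and 0.005/0.02). The second is 1 − exp(−15s). Neither allows for competing first events.
- *The definition changes when trial data meet register data.* Statistical Methods does plan a merge, but no parent protocol is shown. Whether any parent trial excluded these tumours is unknown.
- *The questionnaire fails to record tumour type.* The Medical data form is not shown, and Data collected gives only examples of its questions.
- *These tumours are unrelated to the index disease or its treatment.* The documents do not say so, and the point does not need it.

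**Conclusion.** The point holds as a matter of wording. Three endpoints of the primary objective count invasive basal- and squamous-cell skin carcinoma, and LRRFI treats it as competing.

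The consequence is inflated descriptive event rates, of modest size: by 15 years about 1.6 to 5.4 percentage points, with skin carcinoma the first event in roughly 2-6% of participants. The size rests on an assumed skin-carcinoma rate of 0.2-0.5% per year, on constant hazards, and on a recurrence-only base that puts the DFS figures at the upper end. The LRRFI effect is small, a relative fall of about 1.4-3.3% under further assumed rates. No claim is made about power, type I error or treatment contrasts.

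The change is worth making because it is cheap and the horizon is long.

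**What to change.** In the Protocol, Objectives and endpoints of the survey:

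1. Add *excluding basal-cell and squamous-cell carcinoma of the skin* to the second-primary component of DFS, iDFS and DDFS, and to the second-primary item among the LRRFI competing events.
2. State which rule applies to events taken from a parent trial that used a different one. Without this, the exclusion would itself create a change of definition for any parent trial that counted these tumours.

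Then confirm that the Medical data form captures the site or type of any new cancer, so that the rule can be applied to self-reports.

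The cost is one clause in four definitions, one sentence on carried-over events, and a check of the form (one added item if site or type is not already there). The downside is slightly fewer events.

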## Population

Investigators should consider each of the eligibility criteria outlined below when selecting a patient for this register study. In general, participation in a clinical cancer trial thereby meeting the inclusion criteria of the clinical trial where patients were initially enrolled is the essential prerequisite for enrolment into this register study. Further inclusion criteria for participating in the Register for long-term observation are listed below. In connection with participating in clinical cancer trials, patients will be offered to participate in the Register for long-term observation of study participants. Patients may participate in the study regardless of their native language, provided that understanding of the study's purpose is ensured and unequivocal written informed consent can be obtained. It is aimed at including a maximum number of former trial participants in a continuous manner. Therefore, the number of participants enrolled in this register study is dependent on the number of participants in the

initial cancer trials. Because the register study will be analyzed in a descriptive manner, a sample size calculation defining a minimum of participants required is not applicable. An amount of more than 10.000 participants is expected.

### ***Inclusion Criteria***

Patients will be eligible for study participation only if they comply with the following criteria:

1. Participation in a cancer clinical trial.
2. 18 years of age or older
3. Provision of written informed consent

### ***Exclusion Criteria***

1. History of significant neurological or psychiatric disorders or any other condition that would prohibit the understanding of the study purpose and giving informed consent.

### ***Finance and Insurance***

The study will be funded by GBG Forschungs GmbH.

Since there are no study-specific interventions or on-site visits in this study, insurance is not applicable.

### ***Expense Allowance***

There will be no expense allowance paid to participants.

## Methods

### Study Overview

This is a prospective and retrospective, multicenter, register study with a non-interventional design. The study will collect clinical data on long-term patient reported outcomes and further parameters, including but not limited to, pregnancies of former study participants of prospective cancer clinical trials. It is aimed at including a maximum number of former trial participants in a continuous manner. A definite timepoint for the end of this register study is not planned and dependent on the end of the last clinical cancer with participants to be enrolled in self-reporting.

[figure not shown]
The register study is designed to enable the systematic collection of self-reported long-term follow-up data from patients previously enrolled in clinical cancer trials. The task of maintaining contact with former patients is to be transferred from the trial centers to an independent central data trustee. The process is structured to ensure compliance with data protection regulations and to maintain data integrity throughout the follow-up period. The workflow includes the following key steps:

1. Patients will be informed about the register study by their treating physician at the study site, and written informed consent for data collection will be obtained.
2. Upon consent, identifying patient data (IDAT), such as name and contact details, are collected and linked to a pseudonymized patient identifier (PatID) which is performed by the site and shared with the data trustee. This enables secure and compliant communication with participants while protecting their identity. Only the data trustee, who is legally and organizationally independent from the GBG, has access to IDAT and is responsible for it.
3. Follow-up questionnaires are sent to participants via trustee to collect relevant medical and quality-of-life data. Completed pseudonymized questionnaires are returned and used to update the patient's follow-up status and medical data (MDAT) in the GBG Electronic Data Capture (EDC) system.
4. If a patient cannot be reached by trustee, contact tracking procedures are initiated. Updated contact details are recorded and outdated, or incorrect data are deleted by trustee. Participants who remain unreachable are classified as lost to follow-up by trustee.

The inclusion and registration may occur immediately after consent is obtained.

Data flow is coordinated between the trial siter, data trustee, and GBG Forschungs GmbH. Questionnaires may be sent in print or in electronic form.

Participants may authorize a relative or acquaintance to provide information about their state of health, who will then be contacted in place of the participant. Participants may withdraw their consent at any time.

PatID: PatientID = Pseudonym  
 IDAT: Identifying patient Data (Name, Address)  
 MDAT: Medical Data  
 Database

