## Risk Benefit Assessment

As described above, long-term courses with the collection of data on recurrences, deaths and toxicities are primary or at least secondary endpoints in most prospective clinical cancer treatment trials. Yet follow-up observation is usually limited to 1-5 years for administrative reasons. Moreover, clinical information on i.e. late recurrences, quality of life data years after treatment and following pregnancies (as an indicator for fertility) are also extremely valuable for counseling patients when deciding on neoadjuvant or adjuvant treatments. Also, local therapy trials investigating treatment like radiotherapy or surgical procedures may have impact on long-term oncologic and quality of life outcomes. It is a dilemma that, particularly for local therapy studies, there is often insufficient funding available to collect this long-term data. The collection of this long-term data as part of a pragmatic long-term register study based on self-reported information provides future patients and their treating physicians with valuable consultation content that would otherwise not be available at all. In this respect, the findings from the register study have the potential to have a direct impact on medical care. As there are no study specific procedures or investigations or on-site visits there is no potential harm in participating. Even if individual study participants do not personally benefit from participating in the study, the benefits of register study participation clearly outweigh the risk of participating. As the information that is stored and analyzed within the register study is reported by the respective participants themselves, additional individual medical information is not generated within the register study. Participation in the register study continues until withdrawal of consent, death or lost to follow up. The register study may be prematurely terminated in case of lower patient accrual or lower questionnaire return rate for a longer period that does not allow reliable analysis of the study's objectives.

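### No vital-status outcome precedes loss to follow-up: a death without a named contact person is recorded as a loss, which biases OS upward if losses are censored

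*Protocol*

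**What the plan says.** The protocol's section on objectives and endpoints makes death central: "Overall survival (OS) is defined as the time from randomization to death of any cause". Death from any cause is also an event in DFS, iDFS and DDFS. For LRRFI, distant recurrence, a second invasive cancer "or death from any cause are considered competing events".

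The Study Overview describes how data arrive. In step 3, "Completed pseudonymized questionnaires are returned and used to update" the follow-up status and medical data held in GBG's EDC system. Step 4 covers participants whom the trustee cannot reach. Contact tracking starts, and its only described result is corrected contact details. Otherwise, "Participants who remain unreachable are classified as lost to follow-up by trustee". The Risk Benefit Assessment section adds that the information stored and analysed "is reported by the respective participants themselves".

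Two places go further. The Study Overview and the Data collected section allow a participant to name a relative or acquaintance, who is then contacted instead. The Risk Benefit Assessment section separates death from loss: "Participation in the register study continues until withdrawal of consent, death or lost to follow up".

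**The concern.** A participant cannot report their own death. Where no contact person was named, the described steps offer two results after failed contact: new contact details or loss to follow-up. A participant who has died and one who has moved away then end with the same status. Loss becomes related to the outcome, which is the condition under which ordinary censoring fails.

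If such losses are censored, OS is too high. DFS, iDFS and DDFS are too high wherever the missed death would have been the first event. LRRFI loses competing events. A descriptive survival curve is biased in the same way as one used for a test.

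The point belongs in the protocol because it concerns what is collected and who passes it on. A statistical analysis plan can choose how to handle losses, but it cannot recover deaths that were never collected. GBG is also poorly placed to repair the gap later, since only the trustee holds identifying data.

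**Working it through.** **Setting the passages side by side**

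1. OS needs the fact and date of death (Objectives and endpoints).
2. Follow-up status is updated from returned questionnaires (Study Overview, step 3).
3. After failed contact, the described results are new contact details or loss to follow-up (step 4). No deceased outcome, date of death or message from trustee to GBG is described.
4. A contact person is optional and recorded at the participant's request (Data collected). That person is described as replacing the participant as respondent. Step 4 does not say that this person is asked about vital status before the loss is assigned.
5. Death and loss are distinct ends of participation (Risk Benefit Assessment), but no step says how they are told apart.

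From 2 to 4, a death without a named contact becomes a loss. From 5, this is not what the protocol intends.

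**Size, as an illustration**

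The protocol gives no death rate, loss rate or censoring rule, so there is no figure to reproduce. The inputs are:

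- Yearly death hazard h: assumed constant at 2%, 3% or 4%. The 2-4% per year in the Rationale is a recurrence rate and is not the source.
- Share f of post-trial deaths captured: assumed 0.5.
- Missed deaths: assumed censored close to the time of death.
- Years c with full capture by the parent trial: the Rationale gives usual trial follow-up as 1-5 years, and Statistical Methods says trial data are merged with register data. I take c = 5, with c = 0 as the extreme.

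True 10-year OS = exp(-10h).
Apparent 10-year OS = exp(-[c·h + (10 - c)·f·h]).

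| h | True OS | Apparent, c = 5 | Excess | Apparent, c = 0 | Excess |
|---|---|---|---|---|---|
| 2% | exp(-0.20) = 81.9% | exp(-0.15) = 86.1% | 4.2 points | exp(-0.10) = 90.5% | 8.6 points |
| 3% | exp(-0.30) = 74.1% | exp(-0.225) = 79.9% | 5.8 points | exp(-0.15) = 86.1% | 12.0 points |
| 4% | exp(-0.40) = 67.0% | exp(-0.30) = 74.1% | 7.0 points | exp(-0.20) = 81.9% | 14.8 points |

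With c = 1 and h = 3%, apparent OS is exp(-0.03 - 0.135) = 84.8%, an excess of 10.7 points.

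The result depends strongly on f. At h = 3% and c = 0, apparent OS is exp(-0.27) = 76.3% for f = 0.9 and exp(-0.21) = 81.1% for f = 0.7, against a true 74.1%.

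A Kaplan-Meier simulation with 200,000 participants checked the formula for c = 0, h = 2% and 15 years, censoring missed deaths at the last of an assumed yearly questionnaire. It gave 79.7% with a quarter of deaths missed (formula 79.9%) and 85.9% with half missed (formula 86.1%).

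**The case against.** The strongest reply is that silence in the text is not absence from the plan. The workflow figure is not shown, the Study Overview lists only key steps, the tracking procedures are not spelled out, and the trustee works under a contract. Tracing may well reveal deaths, and the protocol lists death as its own end of participation. All of this stands, and it limits the finding to what the text describes. It does not settle how a death and its date are learned and separated from loss.

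Three stronger readings are tempting, and the documents do not support them:

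- A reader might infer that a death has no route into the database at all. The named contact person is a route.
- A reader might infer from "Updated contact details are recorded and outdated, or incorrect data are deleted by trustee" that the details needed for later tracing are lost. The sentence fits the replacement of wrong details equally well, and the Data collected section keeps data until consent is withdrawn.
- A reader might infer that deaths are censored by rule. The protocol states no such rule. The censoring date and any sensitivity analysis are usual content of an analysis plan, and one may exist.

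It can also be said that the study is descriptive, openly pragmatic, and may be stopped if return rates are too low for reliable analysis. That lowers the severity. It does not remove the bias, because a low return rate does not show how many non-responders have died.

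**Conclusion.** The point holds in limited form and should be fixed. In the visible text, the optional contact person is the only described route for a death. Participants who remain unreachable become losses without a vital-status outcome, although the protocol elsewhere separates death from loss.

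The upward direction for OS follows if losses are censored. The size cannot be derived from the documents. On assumed mortality of 2-4% per year with half of post-trial deaths missed, 10-year OS is overstated by about 4 to 7 points when the parent trial captured the first 5 years. The range of 9 to 15 points is an upper bound under the same assumptions, because it starts under-capture at randomization and ignores deaths already recorded by the trial. It should not be read as the expected bias. Both the mortality rate and the captured share are assumptions. If more deaths are captured than assumed, the bias is smaller; it grows with the length of post-trial follow-up.

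**What to change.** Reword step 4 of the Study Overview so that tracing of a non-responder closes with one of three outcomes: alive with new contact details, deceased with date of death, or untraceable. Where a contact person was authorised, that person is asked for vital status before loss to follow-up is assigned. The trustee sends PatID, vital status and date to GBG, and this updates the EDC system without a questionnaire. Each report states the proportion untraceable. Bring the Study Overview and the Risk Benefit Assessment into line, so that death and loss to follow-up are separate statuses in both.

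The cost is a wording change, one more field in the transfer from trustee to GBG, and a little more trustee administration. Contact tracking already takes place, and the trustee already holds identity and PatID together.
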